The primary objective is to estimate the change of T cell receptor level between pre-SABR and post-SABR. A greater increase in T cell receptor level suggests a greater biological effect. With 10 analyzable patients, the change between pre-SABR and post-SABR could have an estimation precision (half of the 2-sided 90% confidence interval) of 0.58 standard deviation (with appropriate transformation when the distribution of T cell receptor level does not follow a normal distribution).

Sample Size Justification: Approximately 35 patients with medically inoperable stage I NSCLC are treated at Johns Hopkins with SABR per year and 75 patients with medically operable stage I NSCLC treated a year. We have planned an accrual rate of 1-2 patients per month and expect enrollment to be complete within 1 years.

Secondary Objectives:

For all secondary endpoints, descriptive analysis but no formal hypothesis testing will be performed given the nature of exploratory analysis. These summaries will be computed for each evaluable patient at time-points before and after SABR. Plots will be used to show the changes in immune response over time both for each individual. For each patient, comparisons in the pre and post-SABR responses will be compared using paired t-tests (or Wilcoxon signed rank tests if appropriate) for continuous variables and McNemar's test for dichotomous or categorical variables. Associations between immune responses will be explored graphically (e.g. scatterplots, boxplots) and numerically (e.g. correlations, χ^2 tests).

Additional pictorial displays will be explored to evaluate the characteristics of iodine uptake after delivery of SABR in relation to SABR dose gradients.

- d. Early stopping rules.

For the primary objective: To minimize unnecessary intervention, we will monitor the post-SABR core biopsy failure rate by a Bayesian stopping rule. We will accrue patients to a different post-SABR biopsy time point, if the posterior probability of unsuccessful biopsies being larger than 70% is 70% or higher. We assume *a priori* that the post-SABR biopsy has an average of 50% successful biopsies, and there is about 22% chance that the unsuccessful biopsy rate is 70%. Based on such rules, we will assess the feasibility when 5 and 10 patients get biopsy, and determine post-SABR core biopsy is infeasible as inability to estimate T cell receptor level and change the timing of biopsies if none of 5, or less than 2 of 10 successful biopsies are observed.

For the secondary objective: To provide additional safety measures around the post-SABR core biopsy, we will monitor post-SABR core biopsy safety closely with extra caution. In particular, we will monitor the rate of unacceptable toxicity with a Bayesian stopping rule, and stop the accrual if there is sufficient evidence that the underlying rate of unacceptable toxicity is greater than 5%, e.g., the poster probability being 5% or higher is more than 80%. Unacceptable and unexpected toxicity post-SABR core biopsy is defined as life threatening hemoptysis. Life threatening hemoptysis is defined as hemoptysis requiring intubation, embolization, or admission for hypoxia. Assuming a prior that the rate of unacceptable and unexpected toxicity is very rare and has an average of 2% and there is about 11% chance that the risk will be 5% or higher. Such monitoring will stop the accrual whenever there are 2 unacceptable toxicities are observed throughout the study.

8 Risks

- a. Medical risks, listing all procedures, their major and minor risks and expected frequency.

SABR Risks: In appropriately selected patients, SABR is well tolerated with low side effect profile. From prospective trial, 48 Gy in 4 fraction SABR regimen has a 13.3% adverse event rate. This was reported in a phase II study evaluating 48 Gy in 4 fractions in 45 patients who were prospectively followed for a median of 2.5 years after this regimen. Types of side effects included fatigue (11% grade 1), musculoskeletal disorders including pain (7% grade 1), injury including fracture (2% grade 2), respiratory disorders (18% grade 1, 4% grade 2) ³².

Core Biopsy Risks: The patients recruited to this study will receive core biopsies. The major expected toxicities from transthoracic or endobronchial core biopsies include self-limited asymptomatic pneumothorax (<30% with transthoracic biopsies, <2% for endobronchial biopsies), pneumothorax requiring self-limited chest tube placement or intubation (<5% for transthoracic biopsies), hemoptysis (<5%), hemorrhage (<5%), infection or other complication (<1%), and death (rare). Minor risks include pain and bleeding.

Since post-ablative radiation biopsy is not routinely performed, the increased risk of major or minor complications for biopsy after SABR is not well known and will be collected.

DE-CT Risks: There are minor risks of iodinated contrast injections (1% to 5% of headaches, nausea, and dizziness). Anaphylaxis is extremely rare (0.01%). Patients with renal insufficiency or renal dysfunction (creatinine >2 mg/dl) are excluded from the contrast-enhanced dual energy portion of study.

Peripheral Blood Draw Risks. The minor risks from additional peripheral blood draws include pain, bleeding, and infection.

- b. Steps taken to minimize the risks.

To minimize risks:

Patient with stage I NSCLC tumor in an appropriate location for SBRT will be determined by the treating radiation oncologist and will be eligible for enrollment.

Patient with easily accessible tumor for biopsy by transthoracic or endobronchial approach will be determined by an interventional radiologist and/or interventional pulmonologist and will be eligible for enrollment.

Patients with renal insufficiency or renal dysfunction (creatinine ≥ 2 mg/dl) are excluded from the DE-CT portion of the trial, but may be enrolled in the trial.

- c. Plan for reporting unanticipated problems or study deviations.

The SKCCC Compliance Monitoring Program will provide external monitoring for JHUaffiliated sites in accordance with SKCCC DSMP (Version 6.0, 02/21/2019). The SMC Subcommittee will determine the level of patient safety risk and level/frequency of monitoring.

- d. Legal risks such as the risks that would be associated with breach of confidentiality.

All outcomes, laboratory, radiographic, and clinical data gathered in this protocol will be handled and stored according to the Johns Hopkins Hospital data confidentiality regulations using password-protected institutional computers. All patient information will be handled using anonymous identifiers. Access to the database is only available to individuals directly involved in the study. Information gathered for this study will not be reused or disclosed to any other person or entity, or for other research. Once the research has been completed, identifiers will be retained for as long as is required by law and by institutional regulations, and at that point will be destroyed. In the rare event, should there be a breach in confidentiality, it will be handled according to institutional policies.

- e. Financial risks to the participants.

Patients will be responsible their routine medical co-pays for standard of care baseline evaluation, diagnosis, treatment, and follow-up as well as associated housing and travel. Patients will not be responsible for the costs of non-standard of care procedures.

9 Benefits

- a. Description of the probable benefits for the participant and for society.

The patient will receive no known additional therapeutic benefit from enrollment on this trial. However, information obtained from this study would help society better understand how SABR can affect the immune system. This knowledge would provide insight into enhancing future potential combinatorial therapies of SABR with immune modulating agents and novel biomarkers for SABR-induced immune changes. As such, this knowledge may lead to additional future treatment options combining SABR and immunotherapies that may improve the outcomes of future patients with stage I NSCLC.

10 Payment and Remuneration

- a. Detail compensation for participants including possible total compensation, proposed bonus, and any proposed reductions or penalties for not completing the protocol.

There will be no compensation for participants who enroll in this protocol and no penalties for not completing the protocol.

11 Costs

- a. Detail costs of study procedure(s) or drug (s) or substance(s) to participants and identify who will pay for them.

Initial evaluation including CT chest with contrast, PET/CT, blood draw, tumor core biopsies, and pathologic evaluation of mediastinal lymph nodes, in addition to SABR treatment, and follow-up are the standard evaluation and treatment protocol for patients with medically operable stage I non-small cell lung cancer (NSCLC) or for those patients who decline surgery. The costs for the work-up, treatment, and follow-up are covered by the patient's health insurance. The cost of management of toxicity of SABR treatment and post-SABR biopsies will also be covered by the patient's health insurance.

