SABR is thought to cause ablation of all tissue within the target RT field. However immediate post-SABR tumor biopsy specimen has never been evaluated; it is therefore uncertain if immunohistochemistry (IHC) staining will reveal any identifiable remnant cell population in the immediate period after SABR. In this study, TCR sequencing of FFPE tissue is first priority. This is followed by WES of FFPE tissue in priority.

Additional FFPE core tissue will be used to evaluate the presence of leukocytes on Hematoxylin & Eosinophil (H&E) staining. If leukocytes are present, immunohistochemical staining and analysis may include but is not limited to CD4+ T-cells, CD8+ T-cells, PD-L1, and FoxP3 transcription factor.

The presence of specific key tumor infiltration lymphocytes (TILs) will first be assessed with immunohistochemical (IHC) staining of CD4 T-cells and cytotoxic CD8 T-cells. The respective T-cell density will be determined by our pathologists. We will then evaluate the presence of FoxP3, a transcription factor in CD4 T-cells, and PD-L1, a key checkpoint-related cell surface marker, in the tumor. If viable tumor cells are present, pathologists will assign an intra-tumoral and peri-tumoral immune cell infiltrate grade of (0) none, (1) rare (2) focal or (3) severe diffuse infiltration of lymphocytes. Our lung cancer pathologists will designate 3 representative fields to be evaluated by image analysis, which will allow for the data to be reported as a percentage of area (intra- and peri-tumoral) with positive T-cell infiltrate staining. Peri-tumoral versus intra-tumoral infiltrates will be scored, since these staining patterns have been shown to correlate with clinical outcomes. Pathologic response will also be scored as percentage of viable tumor, averaged from 3 areas of the FFPE-core biopsy sample. Drs. [name] and [name] have experience in performing reviewing IHC staining of tissue.

[figure not shown]

Figure 2: Immunofluorescence Pre and Post PD-1 in NSCLC patient with treatment response.

Increase in CD8+ T-cells post treatment

3.3.5: Correlate dual-energy CT imaging characteristics with radiation dose, and early post-SABR pathologic outcomes.

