- On follow-up visits, 120cc of study blood will be obtained and stored on months 3, 6, and 12 months. At the 9 month visit, 20cc of study blood will be obtained.

See Laboratory Manual, and Imaging Manual for details of the procedures.

Treatment Plan

SABR is prescribed a total dose of 48 Gy in 4 daily treatment fractions (preferred) or 50 Gy in 5 fractions (if needed per radiation oncologist's discretion). These are both standard of care SABR doses. The radiation treatment planning, prescription radiation dose, and administration will be determined by the attending radiation oncologist.

Tissue heterogeneity correction should be applied for planning. Daily on-board imaging using 3-dimensional cone beam CT (CBCT) is required before each fraction for stereotactic delivery. Additional 4-dimensional cone beam CT should be taken to verify the tumor coverage before each treatment.

General Concomitant Medication and Supportive Care Guidelines

Given a potential for interaction of high doses of anti-oxidants reducing the efficacy of radiation, the patient should abstain from the concurrent use of high dose over-the-counter vitamins, other alternative therapies, and steroids per the exclusion criteria.

Toxicity Assessments

Safety will be monitored continuously by the study investigators for the enrolled patients until study closure. All toxicities will be graded according to the Common Terminology Criteria for Adverse Events (CTCAE Version 5.0). Refer to CTCAE version 5.0 at

https://ctep.cancer.gov/protocoldevelopment/electronic_applications/docs/CTCAE_v5_Quick_Reference_5x7.pdf

- b. Study duration and number of study visits required of research participants.

Duration of Follow Up

Patients will be required to return for follow-up visits as per study calendar after SABR treatment. Patients will have completed the study on the day of the 1-year follow-up. They will not require additional follow-up on study, but should continue routine follow-up with treating provider.

- c. Blinding, including justification for blinding or not blinding the trial, if applicable.
N/A
- d. Justification of why participants will not receive routine care or will have current therapy stopped.

Duration of Therapy

In the absence of treatment delays due to adverse events, treatment may continue until one of the following criteria applies:

1. Disease progression prior to SABR,

2. Intercurrent illness that prevents further administration of treatment,

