2. Prior thoracic radiation in the region that will be treated by SABR.
3. Patient may not be receiving any other concurrent investigational agents or chemotherapy.
4. Patient may not be receiving or received immunotherapy.
5. Patients may not be on or use steroids within 14 days before radiation, and from the duration of radiation to the time of the post-SABR biopsies and blood samples. The following are

exceptions to this criterion: Intranasal, inhaled, topical steroids, or local steroid injections (e.g., intra articular injection).

6. Female patients who are pregnant from screening to completion of SABR

See Appendix for AJCC 8 NSCLC cancer staging and Screening Procedure Outline.

6 Drugs/ Substances/ Devices

- a. The rationale for choosing the drug and dose or for choosing the device to be used. -N/A
- b. Justification and safety information if FDA approved drugs will be administered for non-FDA approved indications or if doses or routes of administration or participant populations are changed. -N/A
- c. Justification and safety information if non-FDA approved drugs without an IND will be administered. -N/A

7 Study Statistics

a. Primary outcome variable.

Primary Objective: Examine the T-cell receptor profile changes induced in the tumor after SABR. If TCR next generation sequencing analysis of post-SABR tumor is feasible, a significant TCR profile change is defined as a multi-fold increase in the frequency of identified TCR complementarity determining region 3 (CDR3) regions present in post-SABR tumor biopsies when compared to control pre-SABR tumor biopsies.

b. Secondary outcome variables.

Secondary Objectives:

1. Evaluate candidate tumor antigens (mutation associated neo-antigens, MANAs, and tumor associated neo-antigens, TAAs) released from the tumor by SABR.
2. Describe the influx of key tumor infiltrating lymphocytes in the tumor after SABR.
3. Link tumor antigen recognition by activated post-SABR peripheral T-cells with candidate pre-treatment MANAs and TAAs primed by SABR.
4. Evaluate the relationship between dual-energy (DE) CT imaging characteristics, radiation dose, and early post-SABR pathologic outcomes after treatment with SABR.
5. Evaluate the safety of post-SABR biopsies

c. Statistical plan including sample size justification and interim data analysis.

Primary Objective:

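### The plan does not mask pathologists to time point, or fix how the three fields are chosen, when they read lymphocyte infiltrate before and after SABR

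*Combined protocol and SAP*

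**What the plan says.** Section 3.3.4 gives the tissue readings to the site's pathologists:

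- On T-cell density: "The respective T-cell density will be determined by our pathologists".
- On infiltrate, where viable tumor cells remain: "pathologists will assign an intra-tumoral and peri-tumoral immune cell infiltrate grade of (0) none, (1) rare (2) focal or (3) severe diffuse infiltration".
- On the area measurement: "Our lung cancer pathologists will designate 3 representative fields to be evaluated by image analysis". Software then reports the percentage of area with positive staining inside those fields.
- On viable tumor: "Pathologic response will also be scored as percentage of viable tumor, averaged from 3 areas of the FFPE-core biopsy sample".

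The density, grade and area readings serve secondary objective 2: "Describe the influx of key tumor infiltrating lymphocytes in the tumor after SABR". The viable-tumor score is labelled pathologic response and fits secondary objective 4: "Evaluate the relationship between dual-energy (DE) CT imaging characteristics, radiation dose, and early post-SABR pathologic outcomes after treatment with SABR".

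Section 4, item c, is the form heading "Blinding, including justification for blinding or not blinding the trial, if applicable", and it is answered N/A. Item e, on a placebo or untreated group, is also N/A. Section 4a refers procedural detail elsewhere: "See Laboratory Manual, and Imaging Manual for details of the procedures". Those manuals are not among the public documents. Nothing in the protocol describes coded slides, a reading order, a rule for choosing fields, a second reader or an agreement check.

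**The concern.** Density, the 0-3 grade and the choice of fields are all matters of judgement, and the expected direction is set out in advance: the Abstract's hypothesis is that SABR brings T-cells into the tumor. With no control group, the whole of objective 2 rests on the within-patient difference between two biopsies.

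If a reader leans even slightly toward higher grades or richer fields in post-SABR tissue, that lean enters the difference in full. It cannot be separated from a SABR effect afterwards. The protocol (Abstract, Significance) expects its results to inform later trials of SABR with checkpoint antibodies, so an apparent influx that came from reading would have consequences outside this pilot.

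**Working it through.** **The plan's own figure.** Section 7c gives 10 analyzable patients and a 90% confidence-interval half-width of 0.58 SD for the primary T-cell receptor change. Half-width = t(0.95, 9 df)/√10 = 1.833/3.162 = 0.580 SD, which reproduces it. The concern does not dispute this figure, and masked reading would not change it.

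**Illustration 1: a general reading bias.** The documents give no size for reader bias, so b is an assumption, in units of the SD of the paired difference. With no true change, the paired t statistic follows a noncentral t distribution with n − 1 df and noncentrality b√n. The chance that the 90% interval excludes zero is P(|T| > t(0.95, n − 1)).

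For n = 10 (critical value 1.833):

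| Assumed b | b√10 | 90% CI excludes zero | Two-sided 5% paired t-test rejects |
|---|---|---|---|
| 0 | 0 | 10% | 5% |
| 0.3 | 0.949 | 22.7% | 13.6% |
| 0.5 | 1.581 | 42.8% | 29.3% |

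Ten is a ceiling for these readings. Section 3.3.4 puts sequencing first in the call on tissue, stains only if leukocytes are seen, and grades only if viable tumor is present. The same formula with fewer pairs gives:

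- n = 8 (critical value 1.895; noncentrality 0.849 and 1.414): 20% for b = 0.3 and 36% for b = 0.5.
- n = 6 (critical value 2.015; noncentrality 0.735 and 1.225): 17% and 28%.

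**Illustration 2: field choice alone.** A simulation of 20,000 studies with 10 patients and no true change took the three richest of m fields post-SABR and three random fields pre-SABR. Field-to-field SD was assumed to be 0.25 to 1.0 times the SD of the paired difference before field sampling. The shift is in units of that same SD.

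| Candidate fields m | Shift in mean | 90% CI excludes zero |
|---|---|---|
| 6 | 0.17 to 0.71 SD | 14% to 50% |
| 10 | 0.26 to 1.06 SD | 20% to 81% |

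This is an extreme form of selection, but it shows that exact measurement inside the fields does not protect against how they were chosen. In the area measurement the reader's influence lies only in field choice; in the density reading and the grade it is direct. The t-based figures are a guide for the continuous readings and do not describe the four-level grade.

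**The case against.** **The documents do not show that readers know the time point.** A reader might infer it from the N/A under blinding. That item asks about blinding the trial, and N/A is a natural answer for a single-arm study. The Laboratory Manual may cover slide handling. This stands: the supportable statement is that masking is not specified.

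**The order of staining and field choice is not stated.** A reader might infer that fields are picked after the CD4 or CD8 stain is seen. Section 3.3.4 leaves this open and mentions H&E first. This stands too. Equally, choosing fields on H&E would not be a full remedy, because the plan uses H&E to look for leukocytes, so a reader could still favor lymphocyte-rich areas.

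**Viable tumor and the DE-CT analysis.** A reader might place viable tumor under objective 2, or infer that reading bias would distort its relationship with DE-CT. Objective 2 covers lymphocytes only, and a uniform shift in post-SABR scores leaves a correlation across patients unchanged. Distortion would need readings that depend on the DE-CT result, and nothing in the documents suggests that.

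**The endpoint is secondary and exploratory.** Section 7c promises description without formal testing, and its 90% interval is set for the primary outcome. That limits the consequence. It does not dispose of the point: the same section lists paired t, Wilcoxon and McNemar tests, and a biased estimate misleads without a p-value.

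**Masking may fail.** Section 3.3.4 expects SABR to ablate tissue in its field, so the histology may itself reveal the time point. That weakens masking but is no argument against rule-based field selection, which works whether or not the reader guesses.

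**Conclusion.** The point holds as a gap in the method. The protocol neither masks pathologists to time point nor fixes how fields are selected, in an uncontrolled pre/post comparison with a predicted direction. A directional bias would add directly to the change described under objective 2. Percent viable tumor, under objective 4, is read with the same lack of safeguards.

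Its size is unknown. The 23% to 43% range rests on an assumed bias of 0.3 to 0.5 SD, 10 complete pairs, roughly normal differences and no true change. It describes a decision rule that the plan does not set for this endpoint. The documents do not support a claim that biased reading will occur. The primary T-cell receptor sequencing outcome does not depend on these readings. The change is worth making because it is cheap and the bias cannot be repaired after unmasked reading.

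**What to change.** Add to section 3.3.4, with a cross-reference from section 4, item c:

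1. The histology laboratory codes all pre- and post-SABR slides and presents them to the same pathologists in random order, without time point or patient identity.
2. The three fields are taken by a fixed systematic or random grid within the intra-tumoral and peri-tumoral areas, not by reader preference.
3. All densities, grades and viable-tumor scores are locked before the codes are opened.

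If the Laboratory Manual already provides this, a sentence in the protocol citing it is enough.

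The cost is the work of coding and ordering slides. No extra reader, slide or biopsy is needed, and the sample size and the 0.58 SD precision stay as they are. Masking will be incomplete where radiation change is visible, and the report should say so.

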Patients will be recruited through the thoracic oncology clinics at Sidney Kimmel Comprehensive Cancer Center at Johns Hopkins (SKCCC).

Study Process

Upon meeting study inclusion and exclusion criteria, consented patients will be registered and enrolled. Each enrolled subject will be assigned a confidential identification number (IDN).

- Baseline evaluations to confirm stage I NSCLC are to be conducted within 60 days prior to start of SABR.
 1. Medical history and physical
 2. Standard of care diagnostic core biopsies. For patients with who have already have biopsy confirmation of a stage I NSCLC completed and wish to enroll on study, they may consent to have an additional study biopsy obtained prior to SABR.
 3. Standard of care peripheral blood collection
 4. Standard of care imaging work-up including CT scan of the chest with contrast performed with dual-energy acquisition
 5. Standard of care PET-CT

[See Appendix for Study Calendar and Procedures](#) and the following paragraph regarding study visits.

In order to minimize the need for research-only in-person visits, telemedicine visits may be substituted for in person clinical trial visits or portions of clinical trial visits where determined to be appropriate and where determined by the investigator not to increase the participants risks. Prior to initiating telemedicine for study visits the study team will explain to the participant, what a telemedicine visit entails and confirm that the study participant is in agreement and able to proceed with this method. Telemedicine acknowledgement will be obtained in accordance with the Guidance for Use of Telemedicine in Research. In the event telemedicine is not deemed feasible, the study visit will proceed as an in-person visit. Telemedicine visits will be conducted using HIPAA compliant method approved by the Health System and within licensing restrictions.

- Radiation treatment planning scan will be done prior to start of SABR.
- For SABR, a total of 48 Gy will be delivered over 4 consecutive work days or 50 Gy over 5 days.
- Prior to the second SABR treatment, 30ml of study whole blood will be obtained.
- Post-SABR study peripheral blood collection and post-SABR study DE-CT will be conducted in the 0-24 hours preceding the scheduled post-SABR biopsy.

- Post-SABR study biopsy will be conducted on the 5th to 7th day after completion of SABR.
- 100cc of study blood will be obtained and stored 1 month post SABR.

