3. Unacceptable adverse event(s),
4. Patient decides to withdraw from the study, or
5. General or specific changes in the patient's condition render the patient unacceptable for further treatment in the judgment of the investigator.

- e. Justification for inclusion of a placebo or non-treatment group.
N/A
- f. Definition of treatment failure or participant removal criteria.

Withdrawal of Subjects from Study Treatment/On Study

- If incorrectly enrolled, subjects should discontinue study treatment and enrollment.
- Subjects may withdraw consent at any time for any reason.
- Subjects may be dropped from the trial at the discretion of the investigator should any untoward effect occur.
- A subject may be withdrawn by the investigator if enrollment into the trial is inappropriate, the trial plan is violated, or for administrative and/or other safety reasons.
- Subject is determined to have met one or more of the exclusion criteria for study participation at study entry.
- Subjects will be removed from the study if the patient cannot complete the prescribed radiation treatment or obtain post-SABR tissue required for immune analyses.
- The reason for study removal and the date the patient was removed must be documented.

Withdrawal of Consent

Subjects are free to withdraw from the study at any time without prejudice to further treatment. Subjects who withdraw consent for further participation in the study will not receive any additional study tests, but will receive standard of care follow-up to monitor adverse events and tumor control, unless the patient has expressly withdrawn their consent to such follow-up.

A subject who withdraws consent will always be asked about the reason(s) for withdrawal and the presence of any AE. The Investigator will follow up AEs outside of the clinical study.

If a patient withdraws consent, they will be specifically asked if they are withdrawing consent to:

- all further participation in the study including any further follow-up (e.g., survival contact telephone calls)
- withdrawal of consent to the use of their study generated data
- withdrawal to the use of any samples

- g. Description of what happens to participants receiving therapy when study ends or if a participant's participation in the study ends prematurely.

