If the study ends or if a participant's participation in the study ends prematurely, patients enrolled on the trial currently receiving treatment will complete their standard of care protocol treatment, but will not receive additional study biopsy, blood work, or imaging tests. They will return for routine care and follow-up with their treating physician.

Replacement of Subjects

If a subject withdraws from the study, that subject will be replaced. In the circumstance where a study subject does not have the post-SABR biopsy obtained, that subject will be replaced. For patients who do not have the post-SABR biopsy obtained, their data will not be used in the analysis.

Protocol Enrollment Completion

Up to 40 patients will be screened. This study will complete subject enrollment and accrual when there are a total of 10 patients accrued with BOTH pre- and post-SABR biopsies obtained.

5 Inclusion/Exclusion Criteria

Inclusion Criteria

1. Written informed consent obtained from the subject prior to performing any protocol-related procedures, including screening evaluations
2. Age > 18 year
3. Histologically or cytologically confirmed non-small cell lung cancer after initial biopsies
4. Patient with accessible tumor for biopsy by transthoracic or endobronchial approach as determined by an interventional radiologist and or interventional pulmonologist.
5. Patient is to have sufficient initial core biopsy samples for tissue analyses
6. AJCC 8th edition stage I lung cancer (clinical T1a-T2a N0 M0, ≤4cm)
7. Adequate normal organ and marrow function as defined below:

Hemoglobin	≥ 9.0 g/dL
Absolute neutrophil count (ANC)	$\geq 1.5 \times 10^9/L$ (> 1500 per mm 3)
Platelet count	$\geq 50 \times 10^9/L$ ($>50,000$ per mm 3)
Creatinine	≤ 2 mg/dL

for the dual-enhanced CT portion of the study;
Creatinine is not required for inclusion into the trial
8. Patient with tumor amenable to SABR treatment as determined by a radiation oncologist
9. Subject is willing and able to comply with the protocol for the duration of the study including undergoing treatment and scheduled visits and examinations including follow up.
10. Post-menopausal status or negative urinary or serum pregnancy test for female pre-menopausal subjects. Women will be considered post-menopausal if they have been amenorrheic for 12 months without an alternative medical cause.

Exclusion Criteria

1. Primary tumors not amenable to serial core biopsies.

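### The rule that drops patients without an obtained post-SABR biopsy from the analysis makes no exception for the biopsy-safety objective

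*Combined protocol and SAP*

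**What the plan says.** Section 4g, Replacement of Subjects, replaces any patient who has no post-SABR biopsy and adds: "For patients who do not have the post-SABR biopsy obtained, their data will not be used in the analysis". Accrual ends (Protocol Enrollment Completion) with "a total of 10 patients accrued with BOTH pre- and post-SABR biopsies obtained".

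Section 4f has a companion removal rule: "Subjects will be removed from the study if the patient cannot complete the prescribed radiation treatment or obtain post-SABR tissue required for immune analyses".

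Biopsy safety is secondary objective 5 (Sections 2 and 7b). Section 7c gives all secondary endpoints a descriptive analysis in evaluable patients. It does not define evaluable and names no safety set.

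Other parts of the plan take a wider view of safety. Section 4a, Toxicity Assessments, says: "Safety will be monitored continuously by the study investigators for the enrolled patients until study closure". Section 7d stops accrual at two unacceptable toxicities, with no condition that tissue was obtained. Section 8a says that complications of biopsy after SABR will be collected, because their added risk is poorly known.

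**The concern.** The exclusion covers the patient's data and the analysis without qualification. No other sentence sets the population for the final objective 5 summary, so this is the only rule that touches it.

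The patient at issue is one in whom the post-SABR biopsy was begun and then abandoned without tissue. A patient who was never biopsied has no biopsy safety to report. If a complication was the reason for abandoning the procedure, the exclusion depends on the outcome being summarised, and the reported complication rate is too low. The safety stop does not fill this gap: it counts only life-threatening hemoptysis and estimates no rate. The final summary is where the plan would report how often this little-studied procedure causes complications.

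**Working it through.** **1. The plan's precision figure.** Section 7c gives a 90% confidence half-width of 0.58 standard deviations for the paired T-cell receptor change with 10 analysable patients. The paired t interval gives t(0.95, 9 df)/√10 = 1.833/3.162 = 0.5797, so the figure reproduces. It needs tissue at both time points. Leaving patients without tissue out of it is unavoidable and is not criticised here.

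**2. Does the exclusion reach an abandoned attempt?** Section 4a, Study Process, describes the procedure: "Post-SABR study biopsy will be conducted on the 5th to 7th day after completion of SABR". Section 4f uses the verb obtain for the tissue. Read together, a biopsy that is obtained in Section 4g can mean tissue in hand, and an attempt without tissue is then excluded. It can also mean only that the procedure was done, and then such an attempt stays in. The text does not settle which.

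**3. Direction of any bias.** Let p be the true complication rate, a the probability of no tissue given a complication, and b the probability of no tissue given none. Among obtained biopsies the expected rate is

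p(1−a) / [p(1−a) + (1−p)(1−b)].

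This equals p when a = b, and is below p when a exceeds b. The documents give neither a nor b, so I put no numbers into it.

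**4. Illustration.** Because patients without a biopsy are replaced, 10 obtained biopsies are fixed by design and abandoned attempts come on top. Assume one abandoned attempt with one complication, and 10 uneventful obtained biopsies. Exact (Clopper-Pearson) two-sided 95% limits:

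- All attempts: 1/11 = 9.1%. The lower limit is 1 − 0.975^(1/11) = 0.23%. The upper limit is the 97.5% point of Beta(2, 10) = 41.3%.
- Under the exclusion: 0/10 = 0%. The upper limit is 1 − 0.025^(1/10) = 30.8%.

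The intervals overlap widely. The example shows that the one observed event disappears from the report; it does not estimate how large a bias to expect.

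**5. What is not affected.** Continuous monitoring covers enrolled patients. The two-event stop counts toxicities throughout the study. The feasibility rule counts unsuccessful biopsies, and such a failure may be tissue that was obtained but could not be analysed, so it can run alongside the exclusion.

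**The case against.** The strongest answer is that the context points to a narrower meaning. The sentence stands under a heading about replacing patients, just before the target of 10 patients with both biopsies, which is the set for the paired immune analysis. The removal rule in Section 4f says what the tissue is for: immune analyses. The passages most specific to biopsy safety, in Sections 7d and 8a, set no tissue condition. The summary sentence in Section 7c is written with pre- and post-SABR immune measurements in mind and fits a complication count poorly. The study calendar appendix and the institutional monitoring plan are not in the text available to me and may bear on toxicity collection.

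Most of this stands, and an immune-only intent is plausible. It does not remove the point, because the sentence does not say so and the objective 5 population is defined nowhere else. If the narrow meaning was intended, the fix only writes it down.

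A reader might go further and infer that complications in a removed patient would not be collected. Section 4f does say "The reason for study removal and the date the patient was removed must be documented", and Section 4g says of patients whose participation ends early: "They will return for routine care and follow-up with their treating physician". That does not follow. The second sentence concerns patients receiving treatment when the study or their participation ends. It stops further study biopsy, blood work and imaging, but not adverse-event collection. Nor does the first limit what else is recorded.

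**Conclusion.** The point holds as a minor wording defect. Taken literally, the exclusion removes an attempted biopsy without tissue, and any complication of it, from the final descriptive summary for objective 5. The effect is confined to that summary. It arises only if an attempt yields no tissue, the literal reading is applied, and abandonment is related to complications.

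The size of any bias is unknown. A reader might be tempted to derive one from the 50% prior mean for biopsy success in Section 7d, or from the general core-biopsy risk ceilings in Section 8a. The documents do not support that. An unsuccessful biopsy in Section 7d need not be an abandoned one. The Section 8a figures are upper bounds that are not specific to biopsy after SABR, and nothing links those events to loss of tissue.

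A reader might also extend the point to blood and dual-energy CT measures taken before the biopsy. That is a separate question, and no harm from it is shown here.

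**What to change.** Replace the exclusion sentence in Section 4g with wording such as: *Patients without post-SABR tissue are excluded only from analyses that require that tissue; every patient in whom a post-SABR biopsy was attempted, with or without tissue, is included in the objective 5 safety summary, subject to consent.* Report the numbers of biopsies attempted, abandoned and obtained beside the complication rate.

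The cost is one sentence and three counts. No patients or procedures are added, and the 0.58 standard deviation precision and both stopping rules stay as they are. The downside is that the reported complication rate may look less favourable.
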